### 7. SAFETY ASSESSMENTS

## 7.1 Device Safety

Elidah believes that the Elitone device and the proposed protocol present low risk to the subjects. This assessment is supported by the following information:

- Non-significant Risk Device Designation Electrical Neuromuscular Stimulators and Nonimplantable Electrical Incontinence Devices have been designated as non-significant risk devices in FDA guidance document. The Elitone device is represented by both of these product types and carries the same risk profile. The device is not life-sustaining and failure of the device to deliver its intended therapy does not result in any notable clinical consequence.
- Developed within ISO 13485 Certified Quality Management System Elidah maintains ISO 13485 certification as a medical device manufacturer, meaning that development and production of the product adheres to accepted best practices for creating safe devices, including processes for continuous product and process improvement, reporting of complaints and adverse events, and quality control methodologies.
- Independent Device Safety Testing The Elitone device has been tested by a third party laboratories and found to be compliant with the IEC-60601 family of standards (Medical Device Electrical Safety), including sub-standards specific to muscle stimulators and home use medical equipment. The device is also compliant with applicable IEC standards for electromagnetic compatibility.
- **Risk Mitigation by Design** As part of the product development Elidah conducts design and process risk analyses intended to identify potential device safety concerns. The development team can then mitigate these concerns through design modifications and additional testing. Examples include:

- Risks associated with electrical shock initiating from a supply main are mitigated by preventing device operation when the device is charging (i.e. connected to an external power supply) and by minimizing the length of the provided cables.
- The device turns off automatically after 20 minutes.
- A custom cable is used, which deters an individual from using one or more of the components with another device.
- Output intensity is controlled by the user and is adjusted in ≤1mA increments, which limits the degree to which the user can be impacted by a "sudden" change in output intensity. Further, the circuit design limits the maximum current to approximately 50mA, a level consistent with commercially available EMS devices.
- Risk Mitigation by Warnings/Precautions In cases where device safety concerns cannot be suitably mitigated by design, user instruction is provided in the form of warnings and precautions. The warnings/precautions provided in the Elitone User Manual TR-1131-FORM-12) have additionally been baselined against the product labeling for other electrical muscle stimulation devices used to treat incontinence, and aligned with FDA recommendations regarding product labeling. For example:
  - Users are instructed not to use the device while bathing.
  - Users are instructed not to wear the device while driving.
  - Users are instructed not to apply the device to the chest or eyes.
- Alignment with Typical Therapeutic Use This study utilizes the device in a manner that is consistent with the devices performance characteristics and with traditional therapeutic use of electrical muscle stimulators. The selection of up to 20 minutes per day and 12 weeks of treatment (6.2) was intentionally selected as being consistent with the practice of physical therapy, so as not to run the risk of overly fatiguing the pelvic floor muscles.

## 7.2 Risks and Side Effects

Participation in the study will expose the subjects to risks and side effects similar to users of electrical muscle stimulators (EMS) and transcutaneous electrical nerve stimulation (TENS) devices, both of which are low risk devices as evidenced by multiple products cleared for over-the-counter use. Note that many of the warnings and precautions associated with general use EMS and TENS devices (e.g. don't place electrodes over the eye) are less applicable to Elitone due to the anatomic-specific nature of the Elitone device. However, as with most medical devices, use of the product does carry health risks and potential medical side effects. Elidah does not foresee any psychological, financial, or legal risks to the subject associated with participation in the study.

The User Manual (TR-1131-FORM-12) identifies applicable warning and precautions. Each candidate receives a copy of these warnings and precautions as part of providing informed consent (see 11.2). Broadly categorized, these risks and side effects include:

- Electrical Shock The device delivers an electrical current to the body. Misuse of the device
  can result in an unintended shock which can be temporarily painful. Forms of misuse could
  include placing the electrode on another part of the body (e.g. across the chest) or turning the
  device on prior to applying the electrode to the body. The device, uses both hardware and
  software to control the output and has undergone extensive testing. As noted in 7.1, various
  safety measures are present to mitigate these risks.
- Skin Irritation Although the materials used in the electrode are biocompatible and used in similar, commercially available electrodes, there is a risk of skin irritation. This is likely to be observed as persistent redness at the electrode application site, and is likely to resolve upon cessation of use.

• **Muscle Fatigue** – The treatment is intended to exercise the pelvic floor muscles, and the defined treatment regimen is guided by the recommended regimens of other EMS devices. However, some subject may experience notable muscle fatigue, which, in the near-term, could result in a temporary increase in urine leakage. Such occurrences are likely to resolve within a matter of hours.

### 7.3 Adverse Events and Serious Adverse Events

Adverse events are the primary means for assessing device/treatment safety. Adverse events may be identified through direct communication with the subjects and through analysis of study materials.

For all adverse events, sufficient information will be pursued and/or obtained so as to permit (1) an adequate determination of the outcome of the events (i.e., whether the effect should be classified as a serious adverse effect) and (2) an assessment of the casual relationship between the adverse event and the device/treatment.

Adverse events determined to be associated with the device/treatment will be followed until they are resolved or stabilized. The CTCAE definitions and scoring of Adverse Events will be used.

An **adverse event (AE)** is generally defined as any unfavorable and unintended symptom or finding which either occurs during the study, having been absent at baseline, or, if present at baseline, appears to worsen during the study. Adverse events are recorded regardless of their relationship to the study intervention.

A **serious adverse event (SAE)** is generally defined as any adverse event that results in death, is life threatening, requires inpatient hospitalization or prolongation of existing hospitalization, results in persistent or significant disability/incapacity, or is a congenital anomaly: Grades 3-5.

## 7.4 Reporting Procedures

Subjects are instructed to report adverse events at the time of occurrence via either phone or email. Adverse events may also be identified during routine communication with the subject (e.g. 6th week follow-up) or review of the subject's Daily Log.

The Data Safety and Monitoring Board will use the following 0 to 5 scale to grade adverse events (AE): 0 = none or event is not clinically significant, 1 = mild AE that does not require treatment, 2 = moderate AE that does require treatment, but resolves completely, 3 = severe AE (e.g. one that results in temporary inability to conduct one or more everyday activities and requires ongoing medical attention), 4 = life threatening or results in permanent inability to conduct one or more everyday activities, and 5 = death.

In the event of an AE rated ≥2 the Clinical Director will instruct the subject to obtain medical treatment from a qualified healthcare professional. If the subject becomes ill or is physically injured due to the use of the Elitone™ device, she will not be responsible for the costs required to diagnose or treat such injury. The costs of diagnosis and medical care for any complication, injury, or illness caused by the study device or properly performed non-standard of care investigational procedure required by the study will be covered by Elidah, as long as the subject has followed the study protocol. The subject will not lose any of her legal rights and she does not release Elidah and the study staff from liability for mistakes or intentional misconduct by participating in the study.

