#### 2.2 Primary Endpoint

Treatment efficacy is assessed by comparing the average number of stress urinary incontinence episodes per day at the end of treatment to the corresponding pre-treatment number.

Safety is determined by review of Adverse Events as defined in 7.3, and determination of no serious adverse event during the study.

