## 6.6 Control/Sham Device

Subjects in the control group will receive a sham device that is identical to the Elitone device except for the firmware parameters that define the stimulation waveform and therapy session.

The stimulation waveform for the sham occurs as a higher frequency and lower current, and the treatment session duration is also reduced. These parameters and intended to elicit a surface sensation, but not to induce contraction of the pelvic floor muscles or to have a therapeutic benefit.

As part of the post-study surveys subjects will be asked to describe any sensation they felt, whether they felt any contraction of the pelvic floor, and whether they believe they received a treatment or a sham device. The Data Safety and Monitoring Board will review the Case Repot Forms of any subjects in the control group who report contraction of the pelvic floor muscles (see 10.5)

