#### 9.3 Blinding

Subjects will be blinded to their treatment group. As described in 6.6, with the exception of the firmware loaded on the Controller component, the devices used in the active and control groups are identical, so visualization and handling of the device by the subject will not compromise the blinding. The devices in both groups generate an electrical output that is perceived by the subject, which reduces the risk of subjects identifying themselves as in the control group. The device user manual (TR-1131-FORM-12) and subject instructions (TR-1131-FORM-15) have been modified/written to eliminate language that might suggest to a subject that she is one group or the other. Similarly, study personnel will be instructed to avoid use of language that might indicate which group a subject is enrolled.

Randomization as defined in 9.2 is implemented by an individual who does not interact with the subjects. Study staff who interact with the subjects are blinded to the randomization. Note however, that there is a risk that study staff who interact with the subjects may be informed of group assignment based on comments by the subjects during the study (e.g. if the subject

<sup>2 Richardson et al, "Pelvic floor electrical stimulation: A comparison of daily and every-other-day therapy for genuine stress incontinence", Adult Urology, 48(1):110-118, 1996.

describes the stimulation in a way that makes the stimulation identifiable). Such comments would be documented in the subject's Case Report File. This unblinding would have little impact on data integrity as the study personnel is not involved in the reporting of outcome measures.

Study personnel who analyze individual subject data will be blinded to group assignment. For example, baseline and 12th week episodes/day calculations and pad weight measurements will be made for each subject by blinded study personnel. Later, when group analysis is performed, blinding will be necessarily broken due to the unequal enrollment ratio.

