## 10.5 Data and Safety Monitoring Plan

Elidah will identify a Clinical Director who will be responsible for managing the study and ensuring that the rights and well-being of human subjects are protected, that the reported data are accurate and complete and verifiable from source documents, and that the conduct of the trial is in compliance with the approved protocol, with good clinical practice, and with applicable regulatory requirements. Specific responsibilities of the Clinical Director include:

- Verify that equipment and staff are adequate to safely and properly conduct the study
- Verify that subjects:
  - Meet eligibility requirements
  - Provided informed consent prior to enrollment
  - Are adequately informed about the device use, study requirements and risks of participation
  - Receive all necessary study materials
  - Return all the required data collection forms and specimens
- Verify that, with respect to the device:
  - That shelf-life and storage conditions meet requirements (as applicable)
  - Sufficient supplies (i.e. electrodes, controllers) are sufficient to complete the study
  - That the device is provided only to eligible subjects
  - That the receipt, use, and return of the device is controlled and complies with applicable regulation.
- Verify that source documents and data analyses are accurate and complete
- Verify that adverse events are appropriately reported
- Verify that protocol deviations are appropriately reported

In addition, a Data Safety and Monitoring Board will be established which will review study compliance and adverse events. The Data Safety and Monitoring Board will comprise, at a minimum, the Clinical Director, an individual responsible for technological aspects of the device and an individual with medical training relevant to the used of the device.

Currently, EMS and TENS devices are sold over the counter and used in an at-home environment. Given the high degree of similarity between those devices and the Elitone device, the described level of monitoring is considered appropriate for the low level of risk (see 7).

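### The board that grades adverse events also receives control-identified records, and the masking text names neither the board, the grading nor the relatedness call

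*Combined protocol and SAP*

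**What the plan says.** Section 2.2 makes safety part of the primary endpoint: "Safety is determined by review of Adverse Events as defined in 7.3, and determination of no serious adverse event during the study". Section 7.3 ends its definition of a serious event with "or is a congenital anomaly: Grades 3-5", and section 7.4 gives the grading to the board: "The Data Safety and Monitoring Board will use the following 0 to 5 scale to grade adverse events (AE". Section 7.3 also requires a causality assessment for every adverse event, without naming the assessor. Under 9.4, a serious event related to the device or treatment halts the study until the safety issue is addressed.

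On membership, 10.5 says "The Data Safety and Monitoring Board will comprise, at a minimum, the Clinical Director", plus one person responsible for the device technology and one with relevant medical training. The sponsor identifies the Clinical Director, who manages the study. No member has to be independent.

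Section 6.6 gives the board a second task, to "review the Case Repot Forms of any subjects in the control group who report contraction of the pelvic floor muscles". Section 5.5 gives it a third, the review of non-adherent subjects during data analysis. The session minimum for the first six weeks is stated there for the active group.

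On masking, 9.3 says "Study personnel who analyze individual subject data will be blinded to group assignment" and gives episodes per day and pad weight as examples. It also masks staff who interact with subjects. Section 5.7 masks those who analyse data at subject level. Both sections say that group analysis breaks the blind.

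**The concern.** Severity at the boundary between grades 2 and 3, and relatedness at any grade, are matters of judgement. The plan gives written masking to the efficacy measures used as examples in 9.3. It gives no equally explicit protection to the judgements behind the primary safety outcome, and it sends the people who grade severity some records that disclose the arm.

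Two things are at stake. The relatedness call decides whether the halt in 9.4 applies, and it is the call most exposed to knowledge of the arm: an event in a subject known to have a sham device invites a different answer from the same event in a subject known to have the active one. The grade can also shift with the arm at the 2/3 boundary. Because the safety criterion is zero serious events, one shifted grade can change the verdict.

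**Working it through.** The plan states no figure on this point, so there is none to reproduce. The check compares the sections and then illustrates how often one grading call would decide the result.

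**Does the grade reach the verdict?** Yes, on the reading that grade 3 or higher counts as serious (7.3), the board assigns the grade (7.4), and the verdict requires no serious event (2.2). Death and hospitalization leave little discretion. The soft boundary is in 7.4: grade 2 needs treatment but resolves fully, while grade 3 involves temporary loss of an everyday activity and continuing medical attention. Section 7.3 adds latitude by stating "The CTCAE definitions and scoring of Adverse Events will be used", while 7.4 writes out its own scale. The two passages need to be reconciled.

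**Does the board see the arm?** For some subjects, yes. The 6.6 review selects on control status, so each form discloses the arm. Section 10.2 requires only active-group subjects to return the controller and has this reconciled on the Case Report Form, which may also disclose it.

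**Could that happen before grading?**
- Events are to be reported when they occur (7.4), whereas the 6.6 information comes from post-study surveys and the 5.5 review takes place during data analysis. Most grading should therefore come first.
- Section 7.4 also allows events to be found by reviewing the Daily Log, and 5.3 has the hardcopy log returned at study end. Such an event could be graded with a control-identified form already in hand.
- Section 9.4 plans interim analyses at 30 and 45 subjects. Nothing keeps group results from board members who still have later events to grade.

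**Does the masking text settle it?** There are two readings.
- Broad: grading adverse events is analysis of individual subject data, so the board is masked. The Clinical Director, who instructs subjects under 7.4, would also be masked as subject-facing staff. Section 6.6 then conflicts with 5.7 and 9.3, because it gives the board control-identified forms.
- Narrow: the text covers calculations like its examples, and nothing masks grading or causality.

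**How often would one call decide?** The inputs are N = 60 (40 active plus 20 control, section 1.5) and an assumed per-subject probability p of a grade 3 or higher event, since the documents give none. All 60 count because 2.2 does not limit the criterion to one arm.

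P(none) = (1 − p)^60; P(exactly one) = 60 × p × (1 − p)^59.

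- p = 1%: P(none) = 0.547; P(exactly one) = 60 × 0.01 × 0.5527 = 0.332.
- p = 2%: P(none) = 0.298; P(exactly one) = 60 × 0.02 × 0.3036 = 0.364.
- Wider range: P(exactly one) is 0.223 at p = 0.5% and 0.145 at p = 5%.
- With N = 80, the upper end of planned enrollment in 5.2: 0.362 at 1% and 0.324 at 2%.

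P(exactly one) is the relevant quantity, because moving a single event across the boundary changes a zero-event verdict only when there is one such event.

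**The case against.** The strongest reply is that the plan already masks the board. Section 5.3 describes the safety measure as an analysis of adverse events, 5.7 and 9.3 mask subject-level analysis, the items in 9.3 are only examples, and 11.3 has study staff communicate by subject number. This is a fair reading. It does not remove the point, because it leaves 6.6 in conflict with the masking text.

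A second reply is that masking does little for a criterion that covers both arms: a serious event on sham also fails it, and a grader with a stake in the device has reason to downgrade whichever arm is involved. This stands. Masking mainly protects relatedness and arm-dependent grading. The general incentive is a question of independence.

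A reader might infer more than the documents support:
- That the board must know the arm whenever it grades. Section 6.6 discloses it only for controls who report contraction, and only after the post-study survey. The 5.5 review is also late.
- That all board judgements are the sponsor's own. Only the Clinical Director is documented as sponsor-chosen, and the employer of the other members is not stated.
- That a planned between-arm comparison of adverse events would be biased. Section 9.5 plans none.
- That one call decides the verdict with probability 33-55%. Those values are 1 − 0.99^40 and 1 − 0.98^40, the chance of at least one event among 40 active subjects. That is a different quantity, in only part of the study population.

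**Conclusion.** The point holds as a gap in bias protection and an inconsistency between sections. It does not show that grading will be unmasked. Whichever way 5.7 and 9.3 are read, they need to be reconciled with 6.6. On the narrow reading, knowledge of the arm may reach severity and relatedness judgements for some subjects.

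The 33-36% figure rests on three assumptions: a 1-2% per-subject rate, independent subjects, and every grade 3 or higher event counting as serious. It measures how often the verdict would turn on one call, not how often that call would be wrong. Section 3.2 reports earlier studies by the sponsor without serious adverse events, so the true rate may be lower. At 0.5% the figure is 22%. The documents do not allow the grading bias to be estimated.

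**What to change.** State in 7.4, 9.3 and 10.5 that the board assigns grade and relatedness from narratives carrying only the subject number. It locks both before it receives any arm-identified record for that subject (the 6.6 review or the 5.5 adherence review) or any group-level result, including interim results. If the arm becomes known earlier, log the unmasking and keep the masked grade on record. Reword 6.6 so that it is consistent with 5.7 and 9.3, and state how the scoring named in 7.3 relates to the scale in 7.4.

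The cost is protocol wording and a small administrative step to strip the arm from narratives, which the existing board can work with. Some narratives may still hint at the arm through the subject's description of the stimulation. The change does not make the board independent.

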## CONFIDENTIAL

### 7.5 Follow-up for Adverse Events

The Clinical Director will follow up all AE rated ≥2 until they are resolved/stable. The Clinical Director will follow procedures of the CAPA system to address the events.

## 8. INTERVENTION DISCONTINUATION

Subjects in the study have the right to discontinue treatment at any point during the study and for any reason. If the subject chooses to discontinue, a reason for discontinuation will be recorded and every effort will be made for the subject to complete the post-study activities defined in Table 5-1.

Elidah may wish to discontinue intervention for a subject for a variety of reasons including those listed below. Effort will be made to bring the subject into study compliance prior to terminating participation.

- Purposeful improper use of the device
- Failure to treat per the assigned schedule
- A recurring adverse event or unanticipated problem.
- Failure to maintain the Daily Log for greater than 2 weeks

A pause on enrollment and/or treatment of active subjects may occur if Elidah discovers a serious issue with the device/treatment (see 7.3). Elidah maintains the right to discontinue the study at any point and for any reason. Stopping treatment does not pose any risk to subjects. The study may be discontinued at any time by the IRB, FDA, or other regulatory or government agency as part of their duties to ensure that research participants are protected.

